8.3 REFERRALS FOR MEDICAL FOLLOW-UP OR PSYCHOLOGICAL COUNSELING

There is a purely theoretical likelihood that stimulation of neuronal circuits can lead to epileptic discharge. To minimize this occurrence, we screen and exclude subjects with personal history of neurological conditions from the study. If abnormalities or a seizure is witnessed during the course of the study, a referral will be made to the UNC Department of Neurology for follow-up. In the theoretical event that a seizure is witnessed that involves the loss of consciousness, the subjects will be told not to operate a motor vehicle until cleared by the DMV.

There is an additional albeit small likelihood that a participant's blood glucose levels at 2 hours may be indicative of impaired glucose tolerance and a possible undiagnosed status of diabetes or prediabetes. Since the GTT is not administered in a medical context or under the supervision of an MD, this is not taken as a conclusive result. Therefore in the event that this occurs, the participant will be contacted by our study diabetes doctor ([name], MD, PhD) or the participant may be referred to follow up with his or her own primary care doctor.

To ensure participant comfort, a study coordinator or research assistant will periodically check in with the participant about any side-effects he/she may be experiencing during each stimulation.

9 DATA AND SAFETY MONITORING

9.1 [name] LAB MONITORING PLAN

The purpose of this monitoring plan is to present the [name] Lab's approach to monitoring clinical trials. The plan facilitates compliance with good clinical practice (GCP):

- a. The rights and well-being of human subjects are protected.
- b. The reported trial data are accurate, complete, and verifiable from source documents
- c. The conduct of the trial is in compliance with the currently approved protocol/amendment(s) with GCP, and with applicable regulatory requirement(s)

This section identifies key monitoring activities and specifies the data to be reviewed over the course of a clinical trial. This is a single site, investigator-initiated, clinical trial, so there will be no site monitoring plan in place.

The latest version of the approved IRB application for this clinical trial will be followed at all times. This responsibility falls into the hands of the study coordinator and research assistants. If at any time there is a deviation from protocol, the deviation from protocol log will be filled out. All team members will be trained on how and when to use this log. The most up-to-date IRB application will be on file in the Clinical Trials office in Room 233 of the Medical School Wing C. Deviations will be sent to the IRB every 4-6 weeks (if necessary).

Periodically, study staff should review 3 randomly selected informed consent forms to ensure that (1) these forms have been filled out appropriately, and (2) the consent form process was followed and properly documented. Should any consent form be in violation, the research team will perform and document a complete review of all consent forms.

AE and SAE are clearly defined in this document. Documents of AE and SAE can be found in the study binder on file in the Clinical Trials office in Room 233 of the Medical School Wing C. It is the responsibility of the study coordinator to report all events to the PI in a timely manner (see 9.3 Reporting Procedures). All AEs and SAEs will be discussed with the PI. For our practices, we have adapted the decision tree provided by the UNC-CH IRB to assist with reporting of such events.

Periodically, the study coordinator should also choose one CRF/eCRF and Source Document to assess for completion and maintenance. In addition, the PI will assess completeness of data on REDCap. The PI has read-only access. This allows the PI to view reports that provide information on any missing data on an individual participant basis, but does not allow the PI to add, change, or input any data. A data safety monitor will review blinded AEs every month.

9.2 SAFETY OVERSIGHT BY THE DSMB

A data safety monitoring board will not be used for this study.

9.3 EARLY WITHDRAWAL OF PARTICIPANTS

9.3.1 REASONS FOR WITHDRAWAL

A study participant will be discontinued from further participation if:

- The participant meets any exclusion criteria (either newly developed or not previously recognized).
- Anything that, in the opinion of the investigator, would place the participant at increased risk or preclude the participant's full compliance with or completion of the study.

Participants are free to withdraw from participation in the study at any time upon request.

9.3.2 DATA COLLECTION FOR WITHDRAWN PARTICIPANTS

We will collect safety data on any participant discontinued because of side effect. In any case, every effort will be made to undertake protocol-specific follow-up procedures. If voluntary withdrawal occurs, the participant will be asked to continue scheduled evaluations and complete an end-of-study evaluation. In the case of an early withdrawal, the researcher will make a note to file indicating this.

9.4 TERMINATION OF STUDY

Participants will be informed of their right to discontinue the study at any time with no penalty. If a participant decides to drop out of the study, either because they cannot tolerate the 75 grams of glucose or they are uncomfortable with the stimulation, the experiment will be immediately stopped. The participant will still be compensated for the entire session. The data from that participant will not be used in analysis. If the participant has already completed either a blood draw or TMS stimulation when they decide to drop out of the study, they will be asked to complete the blood sampling and stimulation questionnaire.

If a seizure occurs at the time of a study visit, a temporary hold will be placed over the study and further investigation will ensue. This could lead to stopping the study prematurely or continuing on with further safety measures in place. If two seizures are witnessed during the study visit, the entire study will be stopped prematurely. These individuals would be referred for further medical attention. It is very unlikely that a seizure will occur.

The study will also be stopped (at least temporarily) if studies provide evidence that transcranial current/magnetic stimulation caused brain damage or other harmful effects on subjects, either short-term or long-term

The IRB will also be informed promptly and provided the reason(s) for the termination of suspension of by the investigator, as specified by the applicable regulatory requirement(s).

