8.2.1 PHYSICAL

Risk of Injury and Discomfort: Non-invasive brain stimulation has been used without any reports of serious side-effects for more than a decade and TMS has been cleared for use in the USA by the FDA. The stimulation made nothing to do with electroconvulsive therapy that applies many orders of magnitude higher stimulation current. Some participants report a scalp pain, tingling, burning, or itching on the stimulation site but no other side effects have been noted. In order to monitor these side-effects, we will be administering side effects stimulation questionnaire after each stimulation session to determine whether these effects were experienced. Research personnel present during these sessions will also check in with the participant periodically during the stimulation to see whether they are comfortable. If any side-effect occurs (rated by the participant as stronger than “moderate”) or the participant is experiencing severe discomfort, the stimulation will be immediately stopped.

Risk of Bleeding: The glucose tolerance test is a medical test in which glucose is given and blood samples taken afterward to determine how quickly it is cleared from the blood. The test is usually used to test for diabetes, insulin resistance, impaired beta cell function, and sometimes reactive hypoglycemia and acromegaly, or rarer disorders of carbohydrate metabolism. We strictly follow the medical guidelines using an FDA-cleared device and sampler and blood sampling will be immediately stopped if any unexpected bleeding occurs.

Risk of Glucose Ingestion: The risks associated with glucose ingestion in healthy participants are minimal.

The potential side effects include nausea, sweating, light-headedness, vomiting, bloating, headache, diarrhea, and constipation. Serious side effects from the test are very uncommon.

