11.1 STATISTICAL ANALYSIS STRATEGIES

Outcome variables include:

Aim 1

- 1) motor-evoked potentials to measure corticospinal excitability (unit: uV)
- 2) TMS-evoked potentials to measure cortical excitability (unit: uV)

Aim 2

- 1) EEG spectral power in the theta-band (4-8Hz) averaged over frontal EEG channels to measure engaged brain network dynamics (unit: dB).
- 2) EEG spectral power in the alpha-band (8-12Hz) averaged over left frontal EEG channels to measure disengaged brain network dynamics (unit: dB).

For all analyses, outcome measures are analyzed as the difference from baseline metrics before the GTT. The repeated measures of primary outcome will be fitted into general linear mixed effect model where baseline measures (continuous), time of measures (categorical), treatment method (binary) and time by treatment as fixed effects, while the within-subject effect among different time point (0, 30, 60, 120, 180 minutes) is modeled as random intercept assuming autoregression model (AR(1)) as covariance structure. The two sided Wald-test of treatment method (fixed effect) between the verum GTT versus control GTT condition is our primary result of interest. We hypothesize a significant main effect for factor GTT but no effect for factor time nor the interaction of GTT by time. We hypothesize that verum-GTT will modulate corticospinal and cortical excitability. In case we do find a significant interaction of GTT by time, we will use post-hoc contrast test to compare the overall differences between verum-GTT versus control-GTT at each time point and correct for multiple comparisons using false discovery rate (FDR) method. All hypothesis tests that are observed to be not statistically significant will be reported as being inconclusive. Based on the nature of our study design, we assume missing data to be minimal, where linear mixed effect model is robust to handle such missing value situations without creating any obvious bias. For all the result tables of statistical analysis, statistical estimates of population parameters will be tabulated along with corresponding confidence intervals (CIs). Given the lack of any comparable study in the literature, we performed a power analysis guided by the number of participants we are able to enroll based on the size of the grant. Briefly, with a sample of N=20 participants, we will be able to detect an effect size of $d_z = 0.66$ with $\alpha = 0.05$ and $\beta = 0.2$. Power analysis was performed with G*Power.

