11.2 CHOICE OF SAMPLE SIZE

The choice of sample size was based on expert opinion and funding limit; we conjecture that 20 participants may be sufficient to provide adequate precision for the estimators of variance components and other parameters for which information is needed to plan a future study. As a rough and indirect assessment of the precision afforded by studying a sample of 20 subjects, we considered that an estimate of the proportion of subjects in the target population that would experience a greater decrease in MEP and TEP amplitude with verum-GTT (Glucose), relative to control-GTT(water) for an observed estimate of 50%, the 95% confidence interval would span [50% ± 20%]. Or, if 80% was the observed estimate, then the 95% CI would span [80% ± 16%].

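### Section 9.4 drops all data of participants who stop for glucose intolerance or stimulation discomfort, although the planned mixed model could use their partial records

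*Combined protocol and SAP*

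**What the plan says.** Section 9.4 concerns a participant who drops out "either because they cannot tolerate the 75 grams of glucose or they are uncomfortable with the stimulation". In that case "the experiment will be immediately stopped", the person is paid for the session, and "The data from that participant will not be used in analysis". No exception is made for a finished session or for readings taken before the stop. A side-effect questionnaire is still requested, so the loss concerns the outcome analysis and not safety reporting.

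Three other sections bear on this:

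- Section 4.1 sets out a two-period crossover, with ten participants taking glucose first and ten taking water first.
- Section 11.1 plans a mixed model on the readings at 0, 30, 60, 120 and 180 minutes. On missing data it says "we assume missing data to be minimal" and that the "linear mixed effect model is robust to handle such missing value situations without creating any obvious bias". It defines no analysis set and does not mention the exclusion in 9.4.
- Section 9.3.2 says: "If voluntary withdrawal occurs, the participant will be asked to continue scheduled evaluations and complete an end-of-study evaluation".

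**The concern.** Intolerance of the glucose load can arise only in the glucose session and only after randomisation. Excluding people for it selects the analysis set towards those who tolerate the drink. The protocol foresees the trigger; section 8.2.1 (Physical) says: "The potential side effects include nausea, sweating, light-headedness, vomiting, bloating, headache, diarrhea, and constipation". Stimulation discomfort can arise in either session, so the exclusion is only partly related to treatment.

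The rule also works against the planned model. A water-first participant who stops in the glucose session has five post-drink water readings and between zero and four glucose readings per outcome. A glucose-first participant who stops in that session has zero to four. A mixed model can use such records, but 9.4 withholds them. The loss also matters for the pilot's stated purpose in section 11.2 of giving "adequate precision for the estimators of variance components and other parameters for which information is needed to plan a future study", because partial records carry information on variance components.

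**Working it through.** **Inputs from the documents.** N = 20, ten per sequence (4.1); d_z = 0.66, two-sided α = 0.05, β = 0.2 (11.1); five post-drink readings per session (11.1). **Not in the documents, so assumed and varied:** number of drop-outs, stopping time, variance ratios, and the correlation between stopping and response.

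**1. The plan's own figure.** For a paired t-test with df = N − 1 and noncentrality d_z√N, N = 20 and d_z = 0.66 give power 0.7995. Solving for 80% power gives d_z = 0.660. The plan's figure reproduces. At the same d_z, power is 0.752 with 18 pairs and 0.694 with 16.

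**2. What the discarded records are worth.** The precision of the time-averaged glucose-minus-water effect was found by generalised least squares (GLS), with a mean for each time-by-drink cell, random subject and session effects, and residual AR(1) of 0 or 0.5. Seven subject:session:residual variance ratios were used: 1:1:1, 1:0.5:1, 1:1:0.25, 0.5:1:1, 1:0.25:2, 2:0.5:1 and 0.25:1:1. Precision is expressed as the equivalent number of complete pairs. This model is close to that of 11.1 but not identical: it adds a session effect and omits the baseline covariate.

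The case with no post-drink glucose reading has a closed form. With m complete pairs, k people who have only the water session, and correlation ρ between a person's two session means,

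n_eq = 2m(m + k) / [2m + k(1 + ρ)].

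Over the variance settings ρ runs from 0.148 (= 0.25/1.695) to 0.741 (= 2/2.7). Two water-first drop-outs (m = 18, k = 2) give 720/(38 + 2ρ) = 18.80 to 18.24. One per sequence (k = 1) gives 684/(37 + ρ) = 18.41 to 18.12. Two glucose-first drop-outs (k = 0) give 18.00.

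Two drop-outs in the glucose session, equivalent pairs with data kept (18 under 9.4):

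| Last glucose reading | Both water-first | One per sequence | Both glucose-first |
|---|---|---|---|
| none | 18.24–18.80 | 18.12–18.41 | 18.00 |
| 0 min | 18.98–19.85 | 18.59–19.16 | 18.18–18.55 |
| 30 min | 19.37–19.92 | 18.83–19.24 | 18.21–18.67 |
| 60 min | 19.64–19.97 | 18.99–19.34 | 18.23–18.74 |
| 120 min | 19.85–19.99 | 19.09–19.39 | 18.23–18.79 |

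Against 0.752 under 9.4, power with one drop-out per sequence is 0.755–0.762 with no post-drink reading and 0.776–0.785 after 60 minutes. The most favourable pattern (both water-first, late stop) approaches 0.799.

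Four drop-outs, two per sequence, against 16 pairs (power 0.694): 16.23–16.80 pairs (0.702–0.718) with no post-drink reading, 17.94–18.64 (0.750–0.768) after 60 minutes, and 18.15–18.76 (0.756–0.771) after 120 minutes. By symmetry, a second-session stop for stimulation discomfort gives the same figures as the water-first column, and a first-session stop the same as the glucose-first column.

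**3. Possible selection bias.** Assume that stopping follows a normal threshold with probability p and correlates r with the glucose-session effect. The completers-only bias in d_z units is then

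r × φ(z_p)/(1 − p) × SD(session)/SD(difference).

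At p = 0.10, φ(z_p)/(1 − p) = 0.1755/0.9 = 0.195, and over the variance settings the SD ratio runs from 0.331 to 0.690.

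- r = 0.3: 0.0585 × (0.331 to 0.690) = 0.019 to 0.040.
- r = 0.5: 0.0975 × (0.331 to 0.690) = 0.032 to 0.067.
- r = 0: zero.

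The sign follows the sign of r, which is unknown. With one drop-out per sequence and all readings kept, none of the bias is removed if stopping precedes any post-drink reading. If stopping follows the 0-minute reading, 30–71% is removed; after the 60-minute reading, 58–85%.

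A separate simulation assumed stronger dependence: a probit slope of 1 per SD on the whole glucose-session response, a correlation of 1/√2 = 0.71. At 10% drop-out it moved a true 0.66 to 0.58–0.59, a bias of 0.07–0.08. For scale, the standard error of d_z at N = 20 is √(1/20 + 0.66²/40) = 0.247.

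**The case against.** The strongest objection is about weight. Every quantity beyond N and d_z is assumed, and nothing in the documents shows that drop-out will be common or related to response. Even so, the main bias range is at most about a quarter of one standard error (0.067/0.247 = 0.27), and the remaining pairs are balanced within person. The upper end of 5 power points needs both drop-outs to be water-first and to stop late; with one per sequence the most is 0.786 against 0.752, about 3.4 points. The remedy does least when intolerance comes earliest. All of this stands, and it keeps the point modest.

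A second objection is that the aims in 2.3.1 are mechanistic, so restricting the analysis to people who took the load is defensible, and that readings after a vomited drink could dilute the effect. That is a fair reason for a sensitivity analysis. It does not justify discarding a finished water session or valid readings taken before the stop.

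Third, 11.1 claims robustness only where missing data are minimal, so it does not strictly contradict 9.4. That is correct. But if drop-outs are rare, keeping their data costs almost nothing, and if they are not, the exclusion matters.

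Fourth, 9.3.2 can be read as the general rule and 9.4 as a specific one. That reading is possible, but the protocol does not state it, and clarification is needed.

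Fifth, the computed model differs from that of 11.1. Analysing the same assumed data without a session effect gave slightly smaller gains (one per sequence, after 0 minutes: 18.59–18.94 against 18.59–19.16 pairs). The conclusion is unchanged.

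**Conclusion.** The concern holds and should be fixed. Section 9.4 states a post-randomisation, partly treatment-related exclusion at participant level, and no other section defines an analysis set that overrides it. That it covers a completed session is the plain reading, though the text does not spell this out.

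The size is small: about 0 to 5 power points with two drop-outs, and a possible bias of 0.02 to 0.07 d_z at 10% drop-out with correlations of 0.3 to 0.5 in either direction. Bias is a possibility, not a demonstrated effect; the risk is selection, not imbalance between conditions. The figures rest on the assumed drop-out numbers, stopping times, variance ratios and correlations. Keeping the data relies on missingness at random, and gains nothing for a first-session stop before any post-drink reading. The plan's sample-size figure is not in question.

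**What to change.** Replace the exclusion sentence in 9.4 with wording such as:

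> Outcome data collected from randomised participants who stop for these reasons, including any completed session and readings taken before stopping, enter the mixed-model analysis. Two sensitivity analyses are reported: one restricted to completers, and one excluding readings after a drink that was not fully consumed or was vomited.

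Report discontinuations with reasons, by drink and session. Do not extend the rule automatically to participants withdrawn under 9.3.1 because they are found to meet an exclusion criterion; state their handling separately. The sponsor must also reconcile 9.4 with 9.3.2 on whether evaluations stop or continue; this review takes no position on which applies.

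Cost: one replaced sentence, one reconciliation, one disposition row, two short sensitivity analyses, and one case-report item on whether the drink was fully consumed and retained, if that is not already recorded. No additional participants are needed.

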10 SAFETY & REPORTING

It is important to assess safety over the course of this study. This section describes in detail how safety is assessed, reporting of side effects and unanticipated problems. This section is a reference for internal use.

10.1 SAFETY PARAMETERS

STIMULATION SIDE EFFECTS. The side effects listed are headache, neck pain, scalp pain, tingling, itching, ringing/buzzing noise, burning sensation, local redness, sleepiness, trouble concentrating, improved mood, worsening of mood, dizziness, flickering lights, and other (specify). Participants are also asked to rate on a 5 point likert scale how related they believe the side effects to be to stimulation (1 = no relation, 2 = remote, 3 = possible, 4 = probable, 5 = definite).

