4 BASIC STUDY DESIGN

Participants who pass an initial screening by phone are asked to attend a screening visit where consent is provided, eligibility for study participation is confirmed and demographic information is collected. Participants who are eligible to participate will then be asked to return for two study sessions after an MRI scan. Sessions will start at 8.00 am and study participants will be asked to fast for the preceding 12 hours and to consume approximately 150g of carbohydrates each day for the 3 days prior to the session. The study procedures are identical for both study visits. The order of the two sessions is equally randomized across participants.

In one visit, an oral 3-hour GTT with a 75g load of glucose will be administered. In the other visit, pure drinking water will be used. Both study visits have the following time-line:

1. Determined the target (hand area of the left precentral gyrus, left primary motor cortex) based on MR images using a TMS neuro-navigation system.
2. Fitting of an EEG electrode net.
3. Baseline EEG and MEP measurements elicited by TMS
4. Measurement of fasting blood glucose level by finger prick
5. Administration of drink (glucose drink or water, 296mL of H₂O for both drinks)
6. Capillary blood draw (finger prick) for glucose level testing and TMS-induced EEG and MEP measurements at 0, 30, 60, 120, 180 minutes after drink administration
7. Digitization of EEG electrodes on the scalp using a camera-type scanner

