4.1 TREATMENT ASSIGNMENT PROCEDURES

Each participant will experience two experimental conditions (glucose drink and water). There are 2 ways to order the two conditions (glucose drink and then water, water and then glucose drink). By randomization, each participant will be assigned to one of the sequences. Ten participants will be assigned to each of these 2 sequence groups. Each session has at least a 3-day gap to minimize the presence of outlasting effects of either the GTT or the TMS. The randomization schedule will be computed prior to recruitment of subjects and the random assignments will be concealed from the personnel who screen potential participants until the moment that the participant is enrolled and ready for baseline evaluations. To accomplish this, the randomization schedule will be used to create a set of sequentially-numbered opaque sealed envelopes.

- Glucose drink → Drinking water (10 participants)
- Drinking water → Glucose drink (10 participants)

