7.2 PREPARATION AND ADMINISTRATION OF STUDY INVESTIGATIONAL PRODUCT

After participants have completed the questionnaire, they will be comfortably seated. The study coordinator and/or the research assistant will be thoroughly trained and have trainings documented on the glucose blood sampling and TMS device and will be present during all sessions. To monitor side effects of blood sampling and stimulation, a questionnaire will be administered after each session.

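### The side-effect form, as described, is built around stimulation, so tolerability of the glucose drink, the only thing that differs between sessions, is captured incompletely

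*Combined protocol and SAP*

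**What the plan says.** The design is a two-period crossover. Section 4.1 gives each participant both a glucose drink and water in randomised order, and section 4 says "The study procedures are identical for both study visits". Stimulation, EEG and finger pricks are therefore common to both sessions.

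Section 8.2.1 (Physical) sets out what the drink may do: "The potential side effects include nausea, sweating, light-headedness, vomiting, bloating, headache, diarrhea, and constipation". Section 9.4 foresees that a participant may leave because the glucose load is not tolerated.

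Section 10.1 contains one safety instrument, headed as covering stimulation: "The side effects listed are headache, neck pain, scalp pain, tingling, itching", continuing through noise, skin, sleepiness, concentration and mood items to "dizziness, flickering lights, and other (specify"). Its only attribution scale, scored 1 to 5, asks participants "how related they believe the side effects to be to stimulation".

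The form's purpose is stated in section 7.2: "To monitor side effects of blood sampling and stimulation, a questionnaire will be administered after each session". Section 8.2.1 describes it as a stimulation questionnaire. Section 9.4 gives participants who drop out a form on blood sampling and stimulation. None of these places names the drink. Section 11 plans no tabulation of side effects by drink condition.

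**The concern.** The checklist asks mainly about the exposure that is the same at both visits, and hardly about the one that is randomised. If it is followed as written, most of the effects that the protocol itself expects from glucose depend on the participant volunteering them. A blank open item is ambiguous: it may mean that the symptom was absent or that nobody thought to write it down. A prompted item answered no is not ambiguous. A volunteered complaint of nausea would then be scored for its relation to stimulation, which is not the likely source.

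Two things are at stake. First, section 11.2 presents this pilot as a source of information for planning a future study, and how well the drink is tolerated is part of that information. Second, the questionnaire part of section 11.1 expects more negative affect and state anxiety after glucose. Without prompted physical symptoms, the team would have little to say about whether such a finding goes together with feeling unwell after the drink.

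**Working it through.** No figure in the plan bears on this point, so there is nothing to reproduce. The check compares two lists in the protocol.

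**Inputs.** (a) The eight glucose effects in section 8.2.1 (Physical). (b) The section 10.1 checklist: headache, neck pain, scalp pain, tingling, itching, ringing or buzzing, burning, local redness, sleepiness, trouble concentrating, improved mood, worsened mood, dizziness and flickering lights. That makes 14 named items, plus one open item.

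**Item by item.**

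| Glucose effect (8.2.1) | Prompt in 10.1 | Relatedness to the drink asked |
|---|---|---|
| Headache | Yes, by name | No |
| Light-headedness | Approximate (dizziness) | No |
| Nausea | Open item only | No |
| Sweating | Open item only | No |
| Vomiting | Open item only | No |
| Bloating | Open item only | No |
| Diarrhea | Open item only | No |
| Constipation | Open item only | No |

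**Count.** Effects without a prompt: 8 − 1 (headache) − 1 (dizziness for light-headedness) = 6 of 8. If dizziness is not accepted as equivalent, the count is 8 − 1 = 7 of 8.

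**Allowing for timing.** The last measurement is 180 minutes after the drink and the form follows the session. Diarrhea and constipation may begin after the participant has left, so a form completed at the visit is a poor instrument for them. Setting those two aside leaves 8 − 2 = 6 effects that the form could reasonably catch. Of these, 6 − 2 = 4 have no prompt: nausea, sweating, vomiting and bloating.

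**Other routes by which a drink effect could be recorded.**

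- Section 8.3: staff check in periodically about any side effects during each stimulation. Measurements fall at 0, 30, 60, 120 and 180 minutes after the drink, so there are five occasions in the relevant period. No symptom list for these check-ins is given.
- Section 9.1: events are reported to and discussed with the principal investigator, and a data safety monitor reviews adverse events monthly. No method of eliciting them is described.
- Section 9.3.2: safety data are collected on anyone discontinued for a side effect.
- Section 10.2.1: this covers unexpected events. Effects already listed in 8.2.1 would not normally qualify by their nature.
- PANAS, STAI and BIS/BAS: these measure affect, anxiety and motivation, not physical symptoms.

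These routes would probably catch a conspicuous event such as vomiting in the laboratory. They do not produce a uniform yes-or-no record of nausea, sweating or bloating for each participant at each session.

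**The case against.** The strongest reply has four parts.

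**The form itself is not shown.** Section 7.2 says it covers blood sampling, yet section 10.1 lists no blood-sampling item. Section 10.1 may therefore describe only the stimulation part. Appendix A refers to side-effects questionnaires in the plural, and Appendix F reproduces none. This stands as a limit: the documents show that drink items are not described, not that the form in use lacks them.

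**The crossover already provides the comparison.** A reader might infer that drink tolerability cannot be compared between conditions at all. The documents do not support that. The form is given after each session and every participant has both drinks, so each listed item, and any free text, can be compared between glucose and water within participant. For the same reason a drink-relatedness rating is not essential: the water session is the control. No blinding of participants to the drink is described, so such a rating would also be open to expectation.

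**Drop-outs are not lost to safety.** A reader might also infer that withdrawals for intolerance cannot be linked to symptoms. Section 9.3.2 provides for safety data in exactly that case and for a note to file on early withdrawal. What remains is narrower: the form that section 9.4 gives at drop-out is, by its name, again about blood sampling and stimulation.

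**Tolerability is not an aim.** The outcomes are MEP, TEP and EEG power in healthy volunteers, and section 8.2.1 calls the risks of glucose ingestion minimal. This stands, and it limits the weight of the point. Physical discomfort caused by glucose would in any case be part of the drink's effect on mood, not a bias in it, and it bears only on the questionnaire hypotheses.

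**Conclusion.** The point holds as one of incomplete capture. As described, the form prompts for one of the eight expected glucose effects by name and one approximately. It leaves six to free text (four if the two late-onset bowel effects are set aside) and asks about relatedness only to stimulation. The primary MEP, TEP and EEG results are not affected, and a partial comparison between drinks is possible with the form as it stands.

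The conclusion rests on two assumptions: that section 10.1 describes the whole checklist, and that participants volunteer symptoms less completely than they answer prompts. The documents give no figure for the second, so the size of any under-recording cannot be stated. If the form in use already contains drink items, what is left is to describe them in the protocol and plan the tabulation.

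This is worth changing because the protocol itself names these effects and foresees intolerance as a reason for leaving, while symptoms not asked about at the visit are hard to recover later.

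**What to change.** 1. Add the drink effects from section 8.2.1 to the checklist in section 10.1, using the same form after both sessions. Nausea, sweating, vomiting and bloating matter most. Diarrhea and constipation can be listed, with the caveat that they may begin after the visit.
2. Name the drink in the stated scope of the form in section 7.2, and in the form given at drop-out in section 9.4.
3. Add to section 11.1 a descriptive table of side effects by drink condition, glucose against water, paired within participant.
4. Optionally, add a relatedness rating for the drink.

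The cost is a few extra checklist items at two visits, taken here as about one minute per session (an estimate, not a figure from the documents), and one descriptive table. The change leaves the drinks, the visit schedule and the primary analysis as they are.
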